 - i. All groups (including control): 30 minutes
- 3. Week 24 (6 months)
 - g. All groups (including control): 1 hour at CCC-SLP and Dentist, total = 2 hours

Treatment timeline

- 1. Initial treatment consults involve educating patients on protocol - occurs 2 weeks after first measurement and successful eligibility screen
 - a. Myo Munchee ONLY group: 15 minutes
 - b. OMT ONLY group: 30 minutes
 - c. Myo Munchee + OMT group: 30 minutes
- 2. Every 2 weeks until week 10 (T10), 8 weeks after initial treatment appointment:
 - a. Myo Munchee ONLY group: 15 minutes
 - b. OMT ONLY group: 30 minutes
 - c. Myo Munchee + OMT group: 30 minutes
- 3. Every 4 weeks after T10 until week 26 (T26):
 - a. Myo Munchee ONLY group: 15 minutes
 - b. OMT ONLY group: 30 minutes
 - c. Myo Munchee + OMT group: 30 minutes

At home timeline

- 1. The exercises prescribed by the CCC-SLP will need to be completed at home outside of therapy appointments
- 2. The weekly and total time commitment over the 6 months
 - a. Myo Munchee ONLY - 6 days/week
 - i. Weekly: 72 minutes/week
 - ii. Total at home time commitment = 31 hours
 - b. OMT ONLY - 6 days/week
 - i. Weekly: 90 minutes OMT exercises.
 - ii. Total at home time commitment = 39 hours
 - c. Myo Munchee and OMT - 6 days/week
 - i. Weekly: 72 minutes Myo Munchee chewing, 90 minutes OMT exercises.
 - 1. Total = 2 hours, 42 minutes
 - ii. Total at home time commitment = 70 hours

Total Time commitment

Enrolling in the study is a 26-week commitment with variation in time commitments for each group.

- 1. Treatment groups
 - a. **Myo Munchee Only:**
 - i. Initial measurement consultation: 1 hour at dentist and CCC-SLP = 2 hours

- ii. T10 and T26 measurement appointments: 1 hour at dentist and CCC-SLP = 4 hours

- iii. Treatment appointments:

- 1. Before T10: 15 minutes every 2 weeks = 1 hour

- 2. After T10: 15 minutes every 4 weeks = 1 hour

- iv. Commitment outside of appointments: Weekly: 72 minutes/week. Total = 31 hours

- v. Total time commitment: approximately **39 hours**

b. Oral Motor Therapy ONLY:

- i. Initial measurement consultation: 1 hour at dentist and CCC-SLP = 2 hours

- ii. T10 and T26 measurement appointments: 1 hour at dentist and CCC-SLP = 4 hours

- iii. Treatment appointments:

- 1. Before T10: 30 minutes every 2 weeks = 2 hours

- 2. After T10: 30 minutes every 4 weeks = 2 hours

- iv. Commitment outside of appointments:

- 1. Oral Motor Therapy: 90 minutes/week. Total = 39 hours

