- v. Total time commitment: approximately **49 hours**

c. Myo Munchee and Oral Motor Therapy:

- i. Initial measurement consultation: 1 hour at dentist and CCC-SLP = 2 hours

- ii. T10 and T26 measurement appointments: 1 hour at dentist and CCC-SLP = 4 hours

- iii. Treatment appointments:

- 1. Before T10: 30 minutes every 2 weeks = 2 hours

- 2. After T10: 30 minutes every 4 weeks = 2 hours

- iv. Commitment outside of appointments:

- 1. Myo Munchee: 72 minutes/week. Total = 31 hours

- 2. Oral Motor Therapy: 90 minutes/week. Total = 39 hours

- v. Total time commitment: approximately **80 hours**

d. Control group

- i. Initial measurement consultation: 1 hour at dentist and CCC-SLP = 2 hours

- ii. T10 and T26 measurement appointments: 1 hour at dentist and CCC-SLP = 4 hours

- iii. Total time commitment: **6 hours**

Measurement and Treatment Timeline

Procedures		^Eligibility criteria screen Week 0 (T0)	Initial treatment consultation - week 2 (T2)	#Treatment Every 2nd week	Week 10 (T10)	#Treatment Every 4th week	Study Completion Week 26 (T26)
Informed Consent		X					
Assessment of Eligibility Criteria		X					
Therapy treatment protocol administration	Myo Munchee ONLY	X	X	X	X	X	X
	OMT ONLY	X	X	X	X	X	X
	Myo Munchee + OMT	X	X	X	X	X	X
	Control	X					
Clinical Measurements	*Patient History	X					
	**Dental	X			X		X
	**Orofacial Myofunctional Dysfunction	X			X		X
	Postural Assessment	X			X		X
	Ankyloglossia	X					X
Questionnaires	Sleep Disorders Inventory for Students - Revised	X			X		X
	***Compliance tracker	X			X		X
Additional data	Exit Interview						X
Adverse Events Evaluation				X	X	X	X

*Patient history form includes previous 3-day diet and medical history (included as part of Sleep Disorders Inventory for Students – Revised)

**Additional question to records any changes to the patient's activities, e.g. started chewing gum

***Compliance tracker: paper form will be completed each month by parent and upload to an online form

#After T10, the treatment appointments switch to every 4 weeks until T26

^Eligibility, Enrollment, Informed Consent, and Initial Data Collection will be performed when enrolled in the study. Treatment group allocation will be made after the patient meets all eligibility criteria.

Patient safety

1. Assessment of Safety Event Report Forms

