- Sleep inventory - <https://www.sleepinventory.com/>
- Children's Airway Screening Taskforce

Patient Recruitment

Patient recruitment process

Refer to Appendix for detailed description

Marketing and advertising materials for recruitment

Informational A4 letters for each individual practice have been developed so patients can read and understand what is required to participate in the study. Refer to Appendix for an example.

Financial Information

Compensation to patients for Participation

The compensation associated with participating in the study will be broken into treatment groups.

1. Myo Munchee only group

- a. Free Myo Munchee device
- b. Follow up measurement appointments at T10 and T26: covered by Myo Munchee
- c. Treatment appointments: all 15-minute appointments covered by Myo Munchee
- d. \$250USD voucher if fulfill these criteria:
 - i. Attend all measurement appointments (3 total)
 - ii. Complete all monthly compliance logbooks (6 total)
 - iii. Attend minimum 6 out of 7 of the 15-minute treatment appointments (7 appointments)

2. OMT only group

- a. \$250USD voucher if fulfill these criteria:
 - i. Attend all measurement appointments (3 total)
 - ii. Complete all monthly compliance logbooks (6 total)
 - iii. Attend minimum 6 out of 7 of the 30-minute treatment appointments (7 appointments)

3. Myo Munchee and OMT group

- a. Free Myo Munchee device
- b. \$250USD voucher if fulfill these criteria:
 - i. Attend all measurement appointments (3 total)
 - ii. Complete all monthly compliance logbooks (6 total)
 - iii. Attend minimum 6 out of 7 of the 30-minute treatment appointments (7 appointments)

4. Control group

- a. Free Myo Munchee device at end of study
- b. \$250USD voucher if fulfill these criteria:
 - i. Attend all measurement appointments (3 total)

The \$250 USD voucher that can be spent at one or split across multiple practices

Costs for Participation

The costs associated with participating in the study will be broken into the treatment groups and to the specific appointments below:

1. Myo Munchee only group

- a. Measurement appointments:
 - i. Initial appointment: billed to patient's insurance provider as an initial evaluation consultation

2. OMT only group

- a. Initial and follow up measurement appointments: billed to patient's insurance provider as an initial evaluation consultation

- b. All treatment appointments: billed to patient's insurance provider as OMT has established therapeutic benefit

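### Scheduled adverse-event evaluations number eight in each treated arm and two in the control arm, so any event table against control would lean towards more recorded non-serious events under treatment

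*Protocol*

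**What the plan says.** The schedule table in the protocol's Measurement and Treatment Timeline has one row for "Adverse Events Evaluation", not split by arm. It is marked in the two-weekly treatment column, at T10, in the four-weekly treatment column and at T26. It is not marked at T0 or T2.

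The Treatment timeline section sets the treatment visits, and each item lists only the three active groups. After the initial consultation at week 2, visits run "Every 2 weeks until week 10 (T10), 8 weeks after initial treatment appointment", then "Every 4 weeks after T10 until week 26 (T26". The table footnote agrees: "After T10, the treatment appointments switch to every 4 weeks until T26".

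For controls, the Total Time commitment section lists the baseline appointment (2 hours), then "T10 and T26 measurement appointments: 1 hour at dentist and CCC-SLP = 4 hours", and closes with "Total time commitment: 6 hours". The only voucher criterion for controls under Compensation is "Attend all measurement appointments (3 total"). Groups A to C must also complete six monthly logbooks and attend most of their treatment appointments.

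The Patient safety section defines adverse events broadly, related to the device or not, and sets a 72-hour limit for passing reports to the Principal Investigator. It does not say when parents are to be asked.

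**The concern.** Adverse-event evaluation is attached to visits that controls do not have. The discomforts that the protocol lists as known are gum irritation and fatigue of the masseter, lip and tongue muscles. These are mild complaints in children aged 3 to 5 and would reach the record mainly through a parent's memory. A parent asked every two to four weeks is likely to report more of them than a parent asked once after 10 weeks and once more after a further 16.

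The no-treatment arm is the trial's only internal source of background event frequency. If background events are under-recorded there, a table of events by arm shows an excess under the device or the exercises even when none exists. This is fixed by the data-collection schedule, and no later analysis can recover events that nobody asked about.

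**Working it through.** **Inputs.** Visit calendar: Treatment timeline and the schedule table. Control visits: Total Time commitment. Appointment counts: Compensation. Recall windows: assumptions, because the protocol gives none.

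**Step 1: check the calendar against the protocol's own counts.**
- Treatment visits that are not also measurement visits: T2, T4, T6, T8 before T10, and T14, T18, T22 after it. 4 + 3 = 7. This matches the voucher criterion "Attend minimum 6 out of 7 of the 15-minute treatment appointments (7 appointments").
- Control time: 3 measurement visits × 2 hours = 6 hours, as stated. No time is left for any other control visit.

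**Step 2: count the adverse-event evaluations.** T2 is not marked.
- Groups A, B, C: T4, T6, T8 (3) + T10 (1) + T14, T18, T22 (3) + T26 (1) = 8.
- Group D: T10 + T26 = 2.
- Ratio 8 / 2 = 4.
- Control intervals: T0 to T10 is 10 weeks; T10 to T26 is 16 weeks.

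The time-commitment lists imply 4 + 4 = 8 treatment visits because they count T26 as one; the voucher list says 7 because it does not. Both give 8 evaluations. The Measurement and evaluation timeline puts the final measurement at week 24 instead of week 26. If that were a separate evaluation visit, treated children would have 9 evaluations and controls still 2 (T10 and week 24). The imbalance remains.

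**Step 3: illustrate the size.** Suppose a parent reports everything from the last *w* weeks before an evaluation and nothing earlier. Coverage is the number of weeks from T2 to T26 (24 weeks) that fall within *w* weeks before at least one evaluation.

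| Assumed recall *w* (weeks) | Treated, weeks covered | Control, weeks covered | Ratio |
|---|---|---|---|
| 2 | 8 × 2 = 16 | 2 × 2 = 4 | 4.0 |
| 4 | 24 (no gap exceeds 4 weeks) | 2 × 4 = 8 | 3.0 |
| 8 | 24 | 2 × 8 = 16 | 1.5 |
| 16 | 24 | 8 + 16 = 24 | 1.0 |

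**Step 4: put the coverage on the scale of a safety table.** Assume the same true rate of 0.05 events per week in every arm. The chance that a child has at least one recorded event is 1 − exp(−0.05 × weeks covered). Treated against control:
- 2-week recall: 1 − exp(−0.8) = 55% against 1 − exp(−0.2) = 18%.
- 4-week recall: 1 − exp(−1.2) = 70% against 1 − exp(−0.4) = 33%.
- 8-week recall: 70% against 1 − exp(−0.8) = 55%.
- 16-week recall: 70% against 70%.

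The count of 8 against 2 follows from the protocol. Steps 3 and 4 rest on assumed recall and an assumed rate and show only a range.

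**The case against.** The strongest reply is that the protocol plans no such comparison. Its outcomes include no safety outcome, Data Analysis names no adverse-event test, and safety reports are assessed one at a time for seriousness, cause and expectedness. Closer contact with children who receive an intervention is a normal choice. All of this stands, and it limits the point to descriptive tables that set treated arms beside control.

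A second reply is that reporting is not confined to scheduled visits, since events in any participant must reach the Principal Investigator within 72 hours. That rule governs forwarding and does not prompt parents. It does mean that some control events may surface between visits, so the coverage figures are illustrative. Serious events would come to light largely regardless of visit frequency.

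Third, the direction is towards over-recording under treatment, so the imbalance would not hide a device harm. With 12 controls the background rate would be imprecise in any case. Both points are fair and keep the severity low.

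A reader might also infer that treated arms will show about three times as many events, or that safety data cannot be compared between any arms. The documents support neither. Three is the value at one assumed recall window in a range from 1.0 to 4.0. Groups A, B and C share the same evaluation dates, so visit count does not distort comparisons among them.

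Nor is equal questioning already in place. The monthly tracker records product usage, and logbooks are absent from the control voucher criteria, so nothing shows that control families complete one.

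**Conclusion.** The point holds as a minor one about data collection. On the protocol's calendar, adverse events are evaluated 8 times in each treated arm and twice in controls, and no other scheduled contact with controls is described. Any table against the no-treatment arm would be biased towards more recorded non-serious events under treatment. The coverage ratio lies between 1.0 and 4.0 for assumed recall windows of 16 down to 2 weeks, and the imbalance disappears only if parents recall everything across a 16-week interval. The protocol does not support a single figure, and it does not support the claim that a planned safety analysis is invalid, because none is stated. Fewer visits come with a no-treatment control; unequal questioning does not have to.

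**What to change.** 1. Add one short adverse-event question with a fixed look-back, identical in all four arms, to a monthly parent form. For Groups A to C it can go on the existing monthly tracker; controls need a new form. The tracker covers one week of product use, so the question needs its own stated look-back.
2. Make completion of the form a control voucher criterion, as the logbooks already are for Groups A to C. Data Management sends no further reminder after one week and then treats the survey as incomplete or missing, so unequal return could otherwise bring the imbalance back.
3. Base any table against control on these forms plus the T10 and T26 evaluations, with the same look-back in every arm. List events found only at treatment visits separately.
4. Do not simply restrict the comparison to events elicited at T10 and T26. Treated families may not repeat what they reported at earlier visits, which could reverse the bias. That restriction is usable only if all arms have the same look-back and events already reported within it are counted.

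**Cost:** about 6 × 12 = 72 short forms from control families, one added question for the others, and no extra visits. Treated parents would still be prompted at their six additional visits (8 − 2), so some residual imbalance should be acknowledged when the table is reported.

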Safety reports will be assessed on the seriousness, causality, and expectedness of the event to the trial treatment(s), intervention(s), investigational medical product(s), investigational medical device(s). The following are known and expected adverse effects, harms, risks, or discomforts associated with trial procedures, treatments, or interventions.

a. Known Adverse Effects

None

b. Known Harms, Risks or Discomforts

Gum irritation

Masseter fatigue

Orbicularis oris fatigue

Tongue fatigue

2. Adverse Events

Any untoward medical occurrence, unintended disease or injury, or untoward clinical signs (including abnormal laboratory findings) in participants, users or other persons, whether or not related to the investigational medical device.

Adverse event reports must be reported to the Principal Investigator within 72 hours. All adverse event reports must be recorded in the [Myo Munchee Protocol 0001 Safety Monitoring Register](#).

3. Adverse Device Effect

An adverse device effect (ADE) is related to the use of an investigational medical device. Including adverse events resulting from insufficient or inadequate Instructions for Use, deployment, implantation, installation, or operation, or any malfunction of the investigational medical device. This definition includes any event resulting from use error or from intentional misuse of the investigational medical device.

ADE must be reported to the Principal Investigator within 72 hours. All adverse event reports must be recorded in the [Myo Munchee Protocol 0001 Safety Monitoring Register](#).

4. Serious Adverse Events

Serious Adverse Events (SAEs) that result in or lead to one or more of the following and the event is not related to the investigational medical product, the trial intervention, or procedures:

- The death of a trial participant.
- A life-threatening illness or injury involving a trial participant.
- A participant's permanent impairment of body structure or body function.
- In-patient or prolonged hospitalization (not for a pre-existing condition or an elective surgery) of a trial participant.

- Medical or surgical intervention to prevent life-threatening illness or injury or permanent impairment to a body structure or function of a trial participant.
- Congenital abnormality or birth defect.

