SAE reports are classified following the safety assessment flowchart. SAE reports are reported to the Principal Investigator within 72 hours for multicenter clinical trials. SAR reports must be recorded in the [Myo Munchee Protocol 0001 Safety Monitoring Register](#).

5. Serious Adverse Device Effects

A Serious Adverse Device Effect (SADE) is an SAE that is related to the investigational medical product, the trial intervention, or procedures. SAR reports are classified following the safety assessment flowchart.

a. Expected Serious Adverse Reaction

A serious adverse reaction by its nature, incidence, severity, or outcome is anticipated and identified in the current version of the investigational medical product or intervention safety information are classified as a SAR report. SAR reports are reported to the Principal Investigator within **72 hours** for multicenter clinical trials. Serious Adverse Reaction reports must be recorded in the [Myo Munchee Protocol 0001 Safety Monitoring Register](#).

b. Suspected Unexpected Serious Adverse Reaction (SUSAR)

A serious adverse reaction by its nature, incidence, severity, or outcome is unanticipated and not identified in the investigational medical product, the trial intervention, or procedures for use safety information are classified as a SUSAR.

Fatal or life-threatening Australian SUSAR reports are reported to the Principal Investigator within 7 calendar days after being made aware of the case follow up information reported within a further 8 calendar days.

All other Australian SUSAR reports are to be reported to the Principal Investigator within 15 calendar days after being made aware of the case follow up information reported within a further 8 calendar days. SUSAR reports must be recorded in the [Myo Munchee Protocol 0001 Safety Monitoring Register](#).

6. Significant Safety Issue (SSI)

A safety issue that could adversely affect participants' safety or materially impact the continued ethical acceptability or conduct of the trial. The Principle Investigator must be notified of all significant safety issues within 15 calendar days of the sponsor instigating or being made aware of the issue. SSI reports must be recorded in the [Myo Munchee Protocol 0001 Safety Monitoring Register](#).

7. Urgent Safety Measure (USM)

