A measure that is taken to eliminate an immediate hazard to a participant's health or safety. Significant safety issues where an urgent safety measure is required to be taken to eliminate an immediate hazard must be classified as a significant safety issue requiring an urgent safety measure. The Principle

Investigator must be notified of any significant safety issues that meet the definition of an urgent safety measure should be notified within 72 hours.

Examples include:

- a serious adverse event that could be associated with the trial procedures and that requires modification of the conduct of the trial.
- a patient population hazard, such as lack of efficacy of an intervention used for the treatment of a life-threatening disease.

USM reports must be recorded in the [Myo Munchee Protocol 0001 Safety Monitoring Register](#).

8. Safety Assessment Flow Chart Investigational Medical Device Trials

[figure not shown]

Image. Flow chart from UNSW Clinical Trial Protocol Template.

9. Register of Clinical Trial Safety Monitoring Reports

A register of all event reports assessed and classified is to be retained by the Principal Investigator.

10. Reporting of Clinical Trial Safety Monitoring Reports

Single case reports of Adverse Events Adverse Reactions, Serious Adverse Events (SAEs), Serious Adverse Reactions (SARs), reports do not need to be reported to the IRB. All single case reports must be recorded in a safety monitoring register.

11. Emerging Safety Issues

If safety concerns are identified, the principle investigator and involved staff members will establish a plan to minimize the time participants may be placed at excess risk of harm.

12. Non-compliance, Protocol Deviation and Serious Breaches of Good Clinical Practice

Protocol Deviation

A protocol deviation is defined as any breach, divergence or departure from the requirements of Good Clinical Practice, the clinical trial protocol, the clinical trial standard operating procedures, or the human ethics approval that does not have a significant impact on the continued safety or rights of participants or the reliability and robustness of the data generated in the research or clinical trial. Protocol deviations are events that do not occur persistently or systematically and do not potentially result in participant harm. Examples of protocol deviations include but are not limited to:

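### Section 4 defines a serious adverse event as unrelated to the trial, while section 5 builds the related serious class from it, so the SADE class is empty as written

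*Protocol*

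**What the plan says.** All the relevant text is in the protocol's Patient safety chapter.

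- Section 1 treats three judgements as distinct: "Safety reports will be assessed on the seriousness, causality, and expectedness of the event". Causality there is to trial treatments and interventions as well as to the device.
- Section 2 defines an adverse event (AE) broadly, "whether or not related to the investigational medical device".
- Section 3: "An adverse device effect (ADE) is related to the use of an investigational medical device". It sets no limit on seriousness.
- Section 4 lists the seriousness criteria and adds a condition on cause: "the event is not related to the investigational medical product, the trial intervention, or procedures". It then says that "SAE reports are reported to the Principal Investigator within 72 hours for multicenter clinical trials", but its register instruction names SAR reports, not SAE reports.
- Section 5: "A Serious Adverse Device Effect (SADE) is an SAE that is related to the investigational medical product, the trial intervention, or procedures". Parts 5a and 5b handle expected and unexpected serious adverse reactions.
- Section 7 gives as an example of an urgent safety measure "a serious adverse event that could be associated with the trial procedures and that requires modification of the conduct of the trial".
- Section 10 mentions adverse reactions without defining them, exempts single case reports from going to the IRB, and states: "All single case reports must be recorded in a safety monitoring register".

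**The concern.** Sections 4 and 5 use the same three terms (product, intervention, procedures) with opposite signs, and section 5 takes the section 4 class as its starting point. A related serious event fails section 4 because it is related, and fails section 5 because it is not an SAE.

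Two things are at stake. First, a tabulation of SAEs that follows section 4 would leave out the serious events judged to be caused by the trial, which are the ones a safety review most needs. Second, the categories carry consequences elsewhere in the chapter. They determine the reporting time, and failure to record or report SAEs is listed as a serious breach. Because single case reports need not go to the IRB, the register and its coding are the main safety record for these children, who are 3 to 5 years old.

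**Working it through.** No figure is involved; the check is one of logic. Write S for an event that meets a seriousness criterion in section 4, and R for an event related to the product, intervention or procedures.

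**As written**

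- Section 4: SAE = S and not R.
- Section 5: SADE = SAE and R = (S and not R) and R = empty.

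Applied to the kinds of serious event that can occur:

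| Serious event | AE (s. 2) | ADE (s. 3) | SAE (s. 4) | SADE (s. 5) |
|---|---|---|---|---|
| Unrelated | yes | no | yes | no |
| Related to the device | yes | yes | no | no |
| Related only to oral motor therapy (OMT) or to study procedures | yes | no | no | no |

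The SADE column has no yes in it, and the SAE column has one only for unrelated events.

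**Against the rest of the chapter**

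- Section 1 assesses seriousness and causality separately; section 4 combines them in one label.
- Section 7 describes an SAE for which R is possible; section 4 excludes it.

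**Children concerned.** The clause in section 4 also names procedures. Controls attend study measurements at T0, T10 and T26, so the definition applies to all 4 × 12 = 48 children, not only to the 3 × 12 = 36 who are treated.

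**With the clause removed**

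- SAE = S.
- SADE = SAE and R = S and R, which is the related subset that section 5 describes. Sections 1 and 7 then agree with section 4.

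**Non-serious related events.** The only named category is the ADE, which is tied to the device. Section 1b lists tongue fatigue among the known harms of trial procedures, treatments or interventions. If judged related, it is an ADE in Group A (device only). In Group B (OMT only, 12 children) it is an AE with causality assessed, but has no named related category.

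**The case against.** The best defence is that the sponsor meant two separate classes: unrelated serious events are SAEs, and related serious events are SADEs with the reaction paths of 5a and 5b. On that reading the fault is loose labelling. That is probably the intent, but section 5 does not say it, and section 7 uses the term SAE in a way that this reading would not allow. The safety flowchart is not shown; whatever it contains, it cannot make the two written definitions compatible.

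Much of the defence does stand, and it rules out several stronger readings that a reader might draw:

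- *A related serious event has nowhere to go.* It is an AE under section 2, an ADE under section 3 if the device caused it, is evidently meant for 5a or 5b, and must be recorded under section 10.
- *The SAR and SUSAR classes are empty too.* Parts 5a and 5b start from a serious adverse reaction and do not require the event to be an SAE first. Only the SADE class is empty by construction.
- *Related harm in Group B is fixed at zero.* Only the ADE label is. Section 1 assesses causality to every intervention, so OMT-related events can still be identified and compared. A device-specific category is not in itself an error.
- *Causality must be judged before seriousness, by staff who know the group.* The chapter sets no order and does not say who judges.

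**Conclusion.** The contradiction between sections 4 and 5 is plain in the current text, and section 7 adds to it. Followed literally, the definitions leave the SADE class empty and confine the SAE class to events judged unrelated, in any of the 48 children.

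The effect on reported counts is conditional. The protocol specifies no SAE table, so the omission holds for any listing that adopts the section 4 definition. A reader might infer that the treated groups are bound to look free of serious harm; the documents do not support that, because the events remain in the register and can be recovered from it. The defect is a classification rule that gives a wrong result if applied, and it should be corrected. The uneven coding of non-serious related events across Groups A, B and C is a secondary point of consistency.

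**What to change.** 1. In section 4, delete the clause on relatedness, so that an SAE is any adverse event that meets a listed seriousness criterion, in any group. Record relatedness as a separate field, naming the device, OMT or a study procedure. Section 5 can then stand as the related subset.
2. In the register sentence of section 4, replace SAR reports with SAE reports.
3. Define the adverse reactions named in section 10 to include OMT-related events, so that Groups A, B and C are coded by one rule.
4. Once the definitions agree, check the reporting times attached to them. AE, ADE, SAE and SAR reports carry 72 hours; Australian SUSAR reports carry 7 calendar days if fatal or life-threatening and 15 otherwise. These need to be read together and reconciled; no view is taken here on which time is right.

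The cost is protocol wording and one field in the safety register. No visits or staff are added. The SAE count may be slightly higher, because related serious events will now be in it.
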